9.1.3 Assessment of Adverse Events by the Investigator

The Investigator will assess all adverse events using the National Cancer Institute CTCAE Version 5.0 grading system.

Causality Assessment

The relationship of an adverse event to the administration of the study drug is to be assessed according to the following definitions:

- **Definite:** An adverse event that is consistent with the suspected type of reaction known for the drug, in line with the reasonable temporal order after treatment, and is alleviated or disappears upon discontinuation of the study drug.
- **Probable:** An adverse event that is consistent with the suspected type of reaction known for the drug, in line with the reasonable temporal order after treatment, alleviates or disappears upon discontinuation of the study drug, but could also be caused by the clinical conditions of the study patient or other factors.
- **Possible:** An adverse event that is consistent with the suspected type of reaction known for the drug, not in line with the reasonable temporal order after treatment, and could also be caused by the clinical conditions of the study patient or other factors.
- **Improbable:** An adverse event that is inconsistent with the suspected type of reaction known for the drug, not in line with the reasonable temporal order after treatment, and could also be caused by the clinical conditions of the study patient or other factors.

- Not related: An adverse event that is inconsistent with the suspected type of reaction known for the drug, not in line with the reasonable temporal order from administration of the study drug, or that can be easily explained by other factors, such as underlying diseases, complication, concomitant drugs, and concurrent treatment.

The following factors should also be considered:

- The temporal sequence from study drug administration-
 - The event should occur after the study drug is given. The length of time from study drug exposure to event should be evaluated in the clinical context of the event.
- Underlying, concomitant, intercurrent diseases-
 - Each report should be evaluated in the context of the natural history and course of the disease being treated and any other disease the patient may have.
- Concomitant drug-
 - The other drugs the patient is taking or the treatment the patient receives should be examined to determine whether any of them might be recognized to cause the event in question.

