9.1.4 Adverse Events of Special Interest

The Investigator will monitor each patient for clinical and laboratory evidence for predefined AESIs throughout the patient's participation in this study.

In Part A, events of pruritus, drug-induced liver injury, and all muscle-related adverse events will be monitored as AESIs during this study; the Investigator will assess and record these events on a separate AESI form. Pruritus will be assessed using a visual analog scale and 5-D questionnaire (degree, duration, direction, disability, and distribution) itch scale at each study visit after screening. See [Appendix C](#) and [Appendix D](#).

In Part B, events of elevation of transaminases and all muscle-related adverse events will be monitored as AESIs during this study; the Investigator will assess and record these events on a separate AESI form.

During the course of the study, additional AESIs may be identified by the Sponsor; the Investigator will assess and record in detail any additional information on AESIs on an SAE form (whether or not the event meets seriousness criteria in Section 9.2), to be submitted within 24 hours of awareness of the event.

Adverse events of special interest must be recorded on the eCRF and sent to the ENYO safety designee via fax or email within 24 hours.

Safety Contact Information

PharmaLex

[contact]

[contact]

Email: [contact]

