3.7.1 Adverse Events (AEs)

An AE is defined as any untoward medical occurrence in a clinical investigation patient administered a pharmaceutical product, which does not necessarily have a causal relationship with this treatment. An AE can therefore be any unfavorable and/or unintended sign (including an abnormal laboratory finding), symptom, or disease temporally associated with the use of an investigational medicinal product, whether or not related to the investigational medicinal product.

For analysis, a treatment emergent AE (TEAE) is defined as a new or worsening AE after the first dose of study drug. Programmatically, this will be identified as any AE with a start date on or after the date of first dose. If part of the date for the onset/end of an AE is missing, but the existing parts allow determination of timing of AE onset relative to the first dose of study drug, then the AE will be classified as treatment-emergent or not per review of the existing parts of the date. If timing of the AE onset/end relative to the first dose of study drug cannot be determined, then the AE will be assumed to be treatment-emergent.

A summary overview of all AEs will be provided, which presents the number and percentage of patients in each treatment group from the Safety Population, including number of events, satisfying each of the following categories:

- Any AE
- Any TEAE
- Maximum severity of TEAEs
- Study drug-related TEAEs
- Maximum severity of study drug-related TEAEs
- TEAEs of special interest:
 - Part A: pruritus, Drug Induced Liver Injury (DILI) and muscle-related

➤ Part B: elevation of transaminases and muscle-related

- All serious AEs (SAEs)
- All serious TEAEs (TESAEs)
- All study drug-related TESAEs
- TEAEs leading to early discontinuation
- TEAEs leading to temporary discontinuation of study drug
- TEAEs leading to dose reduction

AEs will be coded using MedDRA v22. The number and percentage of patients with AEs, including the number of AEs, will be summarized by their MedDRA preferred term within system organ class and treatment group. For patient count summaries, multiple AE events with the same MedDRA coded terms (preferred term and system organ class) from the same patients will only be counted once. Similar summaries will be presented for study drug-related TEAEs and TESAEs.

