The number and percentage of patients with TEAEs will be summarized by reported maximum severity within each MedDRA preferred term within system organ class and by treatment group.

A further summary table for TEAEs by preferred term and system organ class will be provided for patients in the Safety Population who were taking a statin; a separate summary table will be provided for patients in the Safety Population who were not taking a statin. Patients who were and were not taking a statin will be identified from the appropriate stratification variable.

Detailed listings will be provided for all AEs. Separate listings will also be provided for AEs of Special Interest, SAEs, TEAEs leading to early discontinuation, TEAEs leading to temporary discontinuation of study drug and TEAEs leading to dose reduction.

For both Part A and Part B, an additional summary of derived pruritus TEAEs will be provided for the following categories:

- Grade 1 (mild or localized), defined as (severity grade 1 and (flagged as pruritus AESI on the eCRF or preferred term="Pruritus generalised")) or preferred term = "Pruritus"
- Grade 2 (widespread and intermittent), defined as severity grade 2 and preferred term = "Pruritus generalised"
- Grade 3 (widespread and constant), defined as severity grade 3 and preferred term = "Pruritus generalised"

3.7.2 *Pruritus Assessments*

Part A

The pruritus visual analog scale (VAS) and 5-D (degree, duration, direction, disability and distribution) itch scale will be assessed at Days 1, 7, 14, 21, 28, 56, 84 and 98 and also at the ET Visit.

Descriptive statistics for the pruritus VAS and 5-D itch scale will be presented for baseline values and for values and the change from baseline at each post-baseline visit.

Part B

In Part B, pruritus will be reported as any other AE. If a patient reports pruritus, the visual analog scale and the 5-D questionnaire (degree, duration, direction, disability, and distribution) itch scale will be administered. Results will be listed.

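### Minor: the derived pruritus table shows every event coded 'Pruritus' as Grade 1 whatever its severity, and gives flagged events under other terms no row at severity 2 or 3

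*SAP*

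**What the plan says.** SAP 3.7.1 plans, for Parts A and B, an extra summary of derived pruritus TEAEs in three rows.

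- The Grade 1 row, labelled as mild or localized, is "defined as (severity grade 1 and (flagged as pruritus AESI on the eCRF or preferred term='Pruritus generalised')) or preferred term = 'Pruritus".
- The Grade 2 row, labelled as widespread and intermittent, needs severity 2 and the preferred term 'Pruritus generalised'.
- The third row reads "Grade 3 (widespread and constant), defined as severity grade 3 and preferred term = 'Pruritus generalised".

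There is no other row.

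The same section keeps the reported grade in two other places. TEAEs are "summarized by reported maximum severity within each MedDRA preferred term", and "Detailed listings will be provided for all AEs".

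Severity comes from the investigator. Protocol 9.1.3 states: "The Investigator will assess all adverse events using the National Cancer Institute CTCAE Version 5.0 grading system".

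Pruritus is an AESI in Part A only. For Part B the SAP's list is "Part B: elevation of transaminases and muscle-related", and Protocol 9.1.4 agrees: "In Part B, events of elevation of transaminases and all muscle-related adverse events will be monitored as AESIs during this study". That section leaves one opening: "During the course of the study, additional AESIs may be identified by the Sponsor".

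**The concern.** The rows are named Grade 1 to Grade 3, in a trial where every adverse event carries a CTCAE grade, so a reader will take them for the investigator's grades. They are not. The row depends partly on which preferred term the event was coded to, and the rule can only lower or lose a grade.

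This matters because pruritus is the main tolerability problem seen so far. Protocol 1.2.2 gives investigator-reported pruritus in Part A as 5 of 6 patients on 100 mg BID, 3 of 5 on 200 mg QD and 5 of 6 on 400 mg QD, against none on placebo. The Part B titration was introduced because of it (Protocol 5.2). The standard severity table is split by preferred term, so this derived table is the only one specified in SAP 3.7.1 that combines pruritus terms by grade. A reader who wants the overall severity of pruritus by arm will go to it, and could find it disagreeing with the standard table without explanation.

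**Working it through.** The question is what a classification rule does, so the check is to apply the three printed definitions to every combination of preferred term, AESI flag and reported severity (3 × 2 × 3 = 18 cells). The plan gives no figure to reproduce.

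**The rule as printed (SAP 3.7.1)**

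- Grade 1: (severity = 1 AND (flag OR term = 'Pruritus generalised')) OR term = 'Pruritus'
- Grade 2: severity = 2 AND term = 'Pruritus generalised'
- Grade 3: severity = 3 AND term = 'Pruritus generalised'

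**Row in which the event appears**

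| Preferred term | Pruritus AESI flag | Severity 1 | Severity 2 | Severity 3 |
|---|---|---|---|---|
| Pruritus | yes or no | Grade 1 | Grade 1 | Grade 1 |
| Pruritus generalised | yes or no | Grade 1 | Grade 2 | Grade 3 |
| Other term | yes | Grade 1 | no row | no row |
| Other term | no | no row | no row | no row |

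1. All 6 cells for 'Pruritus' fall in Grade 1. Four of them (severity 2 and 3, flagged or not) are shown below the reported grade.
2. All 6 cells for 'Pruritus generalised' fall in the row that matches the reported severity.
3. Flagged events under another term are counted at severity 1 and lost at severity 2 and 3 (2 cells).
4. Unflagged events under another term have no row. Pruritus is not a listed AESI in Part B, so this line is the expected one there unless the sponsor adds pruritus as an AESI.
5. No cell is raised above its reported severity.

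**Alternative reading.** Suppose severity 1 were meant to govern the whole Grade 1 definition. The printed brackets do not support that. It would also be no improvement: 'Pruritus' at severity 2 or 3 would then have no row, and the gap for flagged other-term events would remain.

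**Weight of one patient.** Take a patient whose only severity 2-3 pruritus event is not coded 'Pruritus generalised'. That patient drops out of the Grade 2-3 count.

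- Part B, planned arm of 30 (Protocol 10.2.8): 1/30 = 3.3 percentage points.
- Part A, pooled active group of 6 + 5 + 6 = 17 (denominators in Protocol 1.2.2): 1/17 = 5.9 percentage points.

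These figures are the effect per affected patient. They do not estimate how many patients are affected.

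**Is the case realistic?** Protocol 5.2 describes pruritus in HBV patients on this drug as mild or moderate, and Protocol 9.12.1 describes it across trials as mostly so. If moderate is taken as severity 2 (an assumption), a moderate event coded 'Pruritus' would be printed as Grade 1. Neither document gives severity by preferred term for this study, and neither shows an event under a third term.

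**The case against.** The strongest reply is that the scheme is deliberate. All three labels speak of extent: localized for row 1, widespread for rows 2 and 3. On that view the preferred term stands in for extent, an event not coded as generalised does not belong in a widespread row, and a table called derived is expected to differ from one called reported. The detailed programming specifications are a separate document (SAP section 6) and may hold a footnote or a term list.

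Much of this is fair. Extent may well be the intention, and it would account for the handling of 'Pruritus'. But neither document says so. Nor does it explain the other gap: by admitting flagged events of any term at severity 1, the rule allows for other terms and then drops them when they are more severe. An unseen specification cannot be assumed to change a rule that the SAP states in full.

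It is also true that severity and extent can be found elsewhere. The 5-D scale has a degree item and a body-distribution item. In Part A the VAS and 5-D scores are summarized by visit. In Part B they are collected when pruritus is reported, and then only listed. This limits the harm, but it does not correct the table.

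Two further objections stand. In Part B, a term-based table will always miss an unflagged event under an unnamed term. And the per-patient percentages say nothing about frequency.

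**Conclusion.** The point holds, as a minor one. Followed as written, the rule shows 'Pruritus' at severity 2 or 3 as Grade 1 and leaves flagged other-term events at severity 2 or 3 out of the table. This follows from the printed definitions alone.

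The practical size is unknown and may be zero. It depends on how many severity 2-3 pruritus events were coded to something other than 'Pruritus generalised', which the documents do not report. The first effect is plausible given the described intensity of pruritus. The second is possible but not demonstrated.

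The table by reported maximum severity and the AE listings still carry the investigator's grade. No efficacy result, hypothesis test, analysis population or stopping rule depends on the derived table.

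**What to change.** **Preferred change.** Include every event that is AESI-flagged or carries a pruritus preferred term on a list fixed before database lock. Set the row to the investigator's reported CTCAE severity. Show 'Pruritus' against 'Pruritus generalised' as a separate breakdown, so that the information on extent is kept.

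**If the extent-based scheme is intended.** Rename the rows so that they are not read as CTCAE grades, state that preferred term is used as a proxy for extent, and add a row for severity 2-3 events not coded 'Pruritus generalised'.

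**Cost.** The first option changes one SAP definition, the row labels and one derived variable, all from data already collected. It overlaps in part with the standard severity table and may give less favourable counts. The second costs one sentence, new labels and one extra row.

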3.7.3 Clinical Laboratory Tests

Serum chemistry, hematology, coagulation, lipid and metabolic profile parameters and urinalysis will be collected at the Screening Visit, Days 1, 7, 14, 21, 28, 56, 84, 98, and at the ET Visit (Part A) and at the Screening Visit, Days 1, 14, 28, 42 (ALT, AST, ALP, GGT, and total bilirubin only), 56, 70 (ALT, AST, ALP, GGT, and total bilirubin only), 84, 98, and at the ET Visit (Part B).

See Protocol Appendix B for analytes in the serum chemistry panel, additional chemistry parameters, hematology, coagulation, lipid and metabolic profile, and urinalysis.

The serum chemistry and additional chemistry parameters will be summarized and listed together.

Descriptive statistics of each safety laboratory parameter will be presented for baseline values and for values and the change from baseline at each post-baseline visit.

An additional summary table will be presented for CK over time for the patients in Safety Population who were taking a statin.

Values outside the normal range will be categorized as H (high, i.e. above the normal range) or L (low, i.e. below the normal range) based on the central laboratory's normal reference range. The number and percentage of patients with values outside the normal range will be summarized by parameter for each post-baseline visit.

Shift tables will also be presented for baseline vs. maximum post-baseline values and baseline vs. minimum post-baseline values for ALT, AST, Total Bilirubin and ALP. The shift tables for ALT and AST will include the following categories:

- < lower limit of normal (LLN) or Normal;
- > upper limit of normal (ULN) to $\leq 2 \times$ ULN;
- $> 2 \times$ ULN $\leq 5 \times$ ULN;
- $> 5 \times$ ULN to $\leq 8 \times$ ULN;
- $> 8 \times$ ULN.

The shift tables for Total Bilirubin and ALP will include the following categories:

- < LLN or Normal;
- > ULN to $\leq 1.5 \times$ ULN;
- $> 1.5 \times$ ULN to $\leq 2 \times$ ULN;
- $> 2 \times$ ULN.

ALT, AST, and Total Bilirubin will be assessed using the National Cancer Institute Common Terminology Criteria for Adverse Events (CTCAE). Shift tables will be presented for baseline vs. maximum post-baseline grades. The following categories are based on CTCAE Version 5.0 grading system:

Criteria	Grade 1	Grade 2	Grade 3	Grade 4
ALT increased	>ULN - 3.0 x ULN if baseline was normal; 1.5 - 3.0 x baseline if baseline was abnormal	>3.0 - 5.0 x ULN if baseline was normal; >3.0 - 5.0 x baseline if baseline was abnormal	>5.0 - 20.0 x ULN if baseline was normal; >5.0 - 20.0 x baseline if baseline was abnormal	>20.0 x ULN if baseline was normal; >20.0 x baseline if baseline was abnormal
AST increased	>ULN - 3.0 x ULN if baseline was normal; 1.5 - 3.0 x baseline if baseline was abnormal	>3.0 - 5.0 x ULN if baseline was normal; >3.0 - 5.0 x baseline if baseline was abnormal	>5.0 - 20.0 x ULN if baseline was normal; >5.0 - 20.0 x baseline if baseline was abnormal	>20.0 x ULN if baseline was normal; >20.0 x baseline if baseline was abnormal
Total Bilirubin increased	>ULN - 1.5 x ULN if baseline was normal; > 1.0 - 1.5 x baseline if baseline was abnormal	>1.5 - 3.0 x ULN if baseline was normal; >1.5 - 3.0 x baseline if baseline was abnormal	>3.0 - 10.0 x ULN if baseline was normal; >3.0 - 10.0 x baseline if baseline was abnormal	>10.0 x ULN if baseline was normal; >10.0 x baseline if baseline was abnormal
Note: For purpose of deriving CTCAE grade, normal baseline is defined as a baseline value $\leq 1.0 \times$ ULN, and abnormal baseline is defined as a baseline value $> 1.0 \times$ ULN.				

An eDISH plot will also be provided for the Safety Population.

3.7.4 Vital Signs

Vital signs will be measured at the Screening Visit, Days 1, 7 (Part A only), 14, 21 (Part A only), 28, 56, 84 and 98 and at the ET Visit. Vital signs parameters include SBP, DBP, HR, respiratory rate and body temperature. At each visit, two measurements for blood pressure will be taken, the average of the two measurements will be used in the analysis.

Descriptive statistics of each vital signs parameter will be presented for baseline values and for values and the change from baseline at each post-baseline visit. These will be presented by treatment group for each parameter using the Safety Population.

3.7.5 Electrocardiograms

Single 12-lead ECGs will be performed at the Screening Visit, Days 7 (Part A only), 14, 21 (Part A only), 28, 56, 84 and 98 and at the ET Visit. ECG parameters include HR, PR interval, QRS duration, QT interval, QTcF interval and RR interval.

Descriptive statistics of each ECG parameter will be presented for baseline values and for values and the change from baseline at each post-baseline visit. Overall interpretation will also be summarized at each post-baseline visit. These will be presented by treatment group for each parameter using the Safety Population.

3.7.6 Physical Examinations

A complete physical examination (including general appearance; eyes, ears, nose and throat; head and neck; chest and lungs; cardiovascular; abdomen; musculoskeletal; lymphatic; dermatological; neurological systems; mental status; and extremities) will be carried out at the Screening Visit. Brief, symptom directed physical examinations will be carried out at Days 1, 7 (Part A only), 14, 21 (Part A only), 28, 56, 84 and 98 and at the ET Visit.

A complete listing of the physical examination results will be provided for the Safety Population.

4 ANALYSIS TIMING

4.1 Interim Analysis

Two interim analyses were conducted during the course of the study:

- The first interim analysis was to be performed at the end of the Safety Run-in Period, after the last of the 24 patients randomized in Part A completed Day 28 (Week 4). It was anticipated that at the time of the first interim analysis, approximately 10 patients would have completed Day 84 (Week 12) of Part A. This analysis was completed in November, 2019, when 19 subjects had completed Week 4 and 11 subjects had completed Week 12.
- A second interim analysis was performed when 50% of patients in Part B completed Day 56 (Week 8). This analysis was completed in February, 2021.

Refer to the Interim Analysis Plan for details.

4.2 Pre-final Analysis

Part A: After the database is frozen and exclusions from analysis populations have been finalized, the Part A randomized treatment assignments will be unblinded and the Part A pre-final analysis will be generated.

Part B: Database lock and analysis will occur in two steps as described below. The purpose of conducting the database lock and analysis in two steps is to obtain the primary analysis results of the 12-week treatment period as soon as possible for corporate goals. The trigger for the first step database lock is when the last patient finishes Week 12. Patients will no longer be on treatment for the remainder of the study follow-up period, therefore it is not considered to be a substantial risk to the patients or study data to conduct the primary analysis prior to the final database lock.

1. First step: efficacy analyses up to Week 12 - This analysis will be conducted on all randomized patients when all patients will have all their MRI-PDFF, cT1, and laboratory data up to the Week 12 analysis window collected and validated (i.e. SDV'd, reconciled, and locked). The efficacy analyses will be performed up to the Week 12 time point. In other words, the Analysis Data Model (ADaM) efficacy datasets will only include data through Week 12.

Analyses of MRI-PDFF and cT1 endpoints up to the Week 12 time point will correspond to the final analyses for these endpoints. Any other analyses using MMRM, such as laboratory data, up to the Week 12 time point will not exactly correspond to the final analyses for these endpoints. This is because the analysis model is MMRM and includes

Week 14 time points in the model, which will not be included for the first step database lock. After the final database lock when all Week 14 data is available and added to the MMRM, results for all visits used in the MMRM may change.

The efficacy data to be analyzed up to Week 12 includes MRI-PDFF, cT1, LSM, ALT, LDL-C, and body weight.

The safety analyses will be performed on all safety data collected up to the common cut-off date. For this analysis, the common cut-off date is defined as the date of the first database lock that occurs after the last Week 12 visit. The safety analysis will be updated after the second step database lock.

The safety data to be analyzed includes adverse events and GGT.

Summaries of demographics and disposition will also be provided.

ENYO Pharma and Medpace biostatistics team (including Study Data Tabulation Model [SDTM] programmers) will be unblinded at the time of the first step database lock in order to perform the analysis. The analysis will be conducted in a secure location with limited access in order to maintain the blind for the remainder of the study team.

2. Second step: final analysis - This analysis will be conducted at the end of the study and will consist in the final analysis of efficacy data at time points beyond the Week 12 time point and final safety analysis.

Two database locks will be done:

- First database lock (for first step analysis): will include all available data on all randomized patients up to the common cut-off date as defined above. All data needed for determining the Per-Protocol Population and for the first step analysis described above will be included in the first database lock.
- Final database lock (for second step analysis): will include all data, including follow-up, for all screened patients.

Topline TFLs will be provided approximately 1 week after first database lock and unblinding and the full set of pre-final TFLs will be provided approximately 3 weeks after final database lock.

In addition to TFLs, SDTM data and ADaM data along with associated files will be provided as requested ENYO. The SDTM database includes all subjects from Part A and Part B. The ADaM datasets may separate Part A and Part B subjects.

Associated files may include: annotated CRFs, SDTM specifications, SDTM programs, ADaM specifications, ADaM programs, TFL programs, and Clinical Data Interchange Standards Consortium (CDISC) Define packages for both SDTM and ADaM data.

